9.5.1.5.2 SERIOUS ADVERSE EVENTS AND EVENTS ASSOCIATED WITH SPECIAL SITUATIONS

An SAE is any untoward medical occurrence that at any dose:

- Results in death
- Is life-threatening (ie, the subject was at immediate risk of death from the AE as it occurred; this does not include an event that, had it occurred in a more severe form or was allowed to continue, might have caused death)
- Requires inpatient hospitalization or prolongation of existing hospitalization
- Results in persistent or significant disability/incapacity
- Is a congenital anomaly/birth defect (in the child of a subject who was exposed to the study drug)

Other important medical events that may not be immediately life-threatening or result in death or hospitalization but, when based on appropriate medical judgment, may jeopardize the subject or may require intervention to prevent one of the outcomes in the definition of SAE listed above should also be considered SAEs. Medical and scientific judgment should be exercised in deciding whether expedited reporting is appropriate in such situations.

For this study, the following events should always be considered serious and reportable using the criteria of important medical event if the event does not meet other serious criteria: new onset seizures, ocular herpes.

In addition to the above, events associated with special situations include pregnancy or exposure to study drug through breastfeeding; AEs associated with study drug overdose, misuse, abuse, or medication error. These events associated with special situations are to be captured using the SAE procedures but are to be considered as SAEs only if they meet one of the above criteria. All AEs associated with special situations are to be reported on the eCRF whether or not they meet the criteria for SAEs.

All SAEs must be followed to resolution or, if resolution is unlikely, to stabilization.

The following hospitalizations are not considered to be SAEs because there is no “AE” (ie, there is no untoward medical occurrence) associated with the hospitalization:

- Hospitalizations for respite care
- Planned hospitalizations required by the protocol
- Hospitalization planned before informed consent (where the condition requiring the hospitalization has not changed after study drug administration)
- Hospitalization for administration of study drug or insertion of access for administration of study drug
- Hospitalization for routine maintenance of a device (eg, battery replacement) that was in place before study entry

If possible, a blood sample for the measurement of study drug plasma concentration should be drawn at the first report of an SAE or a severe unexpected AE and at its resolution.

9.5.1.5.3 LABORATORY MEASUREMENTS

Clinical laboratory tests to be performed, including hematology, chemistry, urinalysis, and CSF are summarized in [Table 4](#). Subjects should be in a seated or supine position during blood collection. [Table 6](#), [Table 7](#), and [Table 14](#) show the visits and time points at which blood for clinical laboratory tests and urine for urinalysis will be collected in the study. (revised per Amendment 07)

See [Section 9.3.3](#) for safety criteria for discontinuation from study drug-related to absolute counts of CD4, CD8, and B lymphocytes, and for lymphocyte subset counts. See [Appendix 6](#) for safety criteria for discontinuation from study drug related to absolute lymphocyte counts.

Table 4 Clinical Laboratory Tests

| Category | Parameters |
|-----------------------------|--|
| Hematology | Hematocrit, hemoglobin, platelets, red blood cell count, and white blood cell count with differential (bands, basophils, eosinophils, lymphocytes, monocytes, neutrophils). PT, PTT, and INR (Screening, Baseline, and Visit 21 only) (revised per Amendment 02 and 07) |
| Chemistry | |
| Electrolytes | Bicarbonate, calcium, chloride, phosphate, potassium, sodium |
| Liver function tests | Alanine aminotransferase, alkaline phosphatase, aspartate aminotransferase, gamma glutamyl transpeptidase, direct bilirubin, total bilirubin |
| Renal function tests | Blood urea/blood urea nitrogen, creatinine |
| Other | Albumin, cholesterol, globulin, glucose, lactate dehydrogenase, total protein, triglycerides, uric acid |
| Urinalysis | Bacteria, casts, crystals, epithelial cells, glucose, ketones, occult blood, pH, protein, red blood cells, specific gravity, white blood cells |
| Other | Lymphocyte T and B cell subset analyses (see Table 5). Regulatory T cells (revised per Amendment 04) PBMCs (revised per Amendment 02) Ig analyses (IgG, IgA, and IgM). Viral screen (HCVAb [Hepatitis C] and HbsAg [Hepatitis B]). Viral characterization (including HSV1, HSV2 and CMV, etc.) Serum pregnancy test (females of child bearing potential only) Tuberculosis Interferon Gamma Release Assays Tests for thyroid function (thyroid stimulating hormone, free triiodothyronine and free thyroxin) and vitamin B12 Blood sample for storage for subsequent testing of immune status Cerebrospinal fluid sampling |

Whenever unscheduled lymphocyte subset tests are performed or whenever scheduled lymphocyte subsets are repeated, a CBC with differentials must also be repeated. (revised per Amendment 02)

CMV = cytomegalovirus, HBsAg = hepatitis B surface antigen, HCVAb = hepatitis C virus antibody, HSV = herpes simplex virus, Ig = immunoglobulin, INR = International Normalized Ratio, PBMC = peripheral blood mononuclear cell, PT = prothrombin time, PTT = partial thromboplastin time.

The 8 different surface markers (including but not limited to CD3, CD4, CD8, CD45, CD19, CD16, CD56, and CD14) and absolute lymphocyte counts will be measured in order to provide the lymphocyte subset data as shown in [Table 5](#). In addition, Regulatory T cells will be measured. Current sponsor data supports the literature showing there is an age-related decline in lymphocyte subsets (see [Appendix 5](#)). These data have been used to revise the LLNs for CD4 (T helper cells), CD8 (cytotoxic T cells), and CD19 (B cells) absolute counts to the population-adjusted LLNs of 396, 157, and 74 cells/ μ L, respectively) (revised per Amendments 02 and 04).

Table 5 Lymphocyte Subtypes Inclusive in BD Trucount™

| Cell Type | Cell Surface Markers |
|----------------------|----------------------|
| T lymphocytes | CD3 |
| T helper cells | CD3+, CD4 |
| Cytotoxic T cells | CD3+, CD8 |
| Mature B cells | CD3-, CD19 |
| Natural killer cells | CD3-, CD16, CD56 |
| Macrophages | CD14 |

(Table 5 revised per Amendment 04)

Clinical laboratory tests during all phases of the study will be performed by a central laboratory. All blood and urine samples will be collected and sent to the central laboratory on the day of collection unless otherwise instructed. In cases of a safety concern, blood samples will be split (or 2 samples drawn) to allow a local laboratory analysis in addition to the central laboratory. Laboratory certification as available will be included in the final clinical study report for this study.

A laboratory abnormality may meet the criteria to qualify as an AE as described in this protocol (see [Section 9.5.1.5.1](#) and the case report form [CRF] Completion Guidelines). In these instances, the AE corresponding to the laboratory abnormality will be recorded on the Adverse Event eCRF.

9.5.1.5.4 VITAL SIGNS AND WEIGHT MEASUREMENTS

Vital sign measurements (ie, systolic and diastolic BP [mmHg], heart rate [bpm], respiratory rate [per minute], body temperature [in centigrade], and weight [kg]) will be obtained at the visits designated in [Table 6](#), [Table 7](#), and [Table 14](#) by a validated method. (revised per Amendment 07) Measurements of sitting BP and heart rate will be obtained. All BP measurements should be performed on the same arm, preferably by the same person.

9.5.1.5.5 PHYSICAL EXAMINATIONS

A complete physical examination will be performed at Screening as described in [Section 9.5.1.2.1](#). At Baseline and during the Randomization Phase, routine physical examinations will take place as shown in [Table 7](#) and [Table 14](#). (revised per Amendment 07) These examinations will include the cardiovascular system, respiratory system, and neurological system. Health status will be evaluated by brief evaluation of the eyes, ears, nose, throat, and other physical conditions of note. The subject must be queried regarding changes in physical status since the last examination. A urogenital examination will only be required in the presence of clinical symptoms related to this region. Documentation of the physical examination will be included in the source documentation at the site. Only changes from screening physical examination findings that meet the definition of an AE will be recorded on the Adverse Events eCRF.

9.5.1.5.6 ELECTROCARDIOGRAMS

Electrocardiograms will be obtained as designated in [Table 6](#), [Table 7](#), and [Table 14](#). (revised per Amendment 07) During the Core Study, 12-lead standard ECGs will be recorded

in triplicate (1 minute apart) after subjects have been resting in the supine position for at least 5 minutes. During the Extension Phase, a single 12-lead ECG will be recorded after subjects have been resting in the supine position for at least 5 minutes. If the QTcF is greater than 450 msec on the first single 12-lead ECG, 2 additional 12-lead ECGs will be performed 1 minute apart and the mean of the 3 QTcF values will be calculated. (revised per Amendment 07)

On any study day when ECG, vital signs, and blood samples are taken, these procedures should be conducted in the following order: ECG first, followed by vital signs, and then blood samples.

An ECG abnormality may meet the criteria of an AE as described in this protocol (see [Section 9.5.1.5.1](#)) and the CRF Completion Guidelines. In these instances, the AE corresponding to the ECG abnormality will be recorded on the Adverse Events eCRF.

9.5.1.5.7 SAFETY MRI

Safety brain MRI assessments will be performed at the times shown in [Table 6](#), [Table 7](#), and [Table 14](#). (revised per Amendment 07) Additional safety MRI scans can be performed at UNS Visits if clinically necessary. MRI acquisition and interpretation will be organized centrally to ensure reproducibility and consistency between units involved.

Safety MRIs will be acquired using a standardized procedure that will include fluid-attenuated inversion recovery (FLAIR), gradient-echo, T1, and diffusion-weighted sequences to determine the presence of focal lesions including, but not limited to, evidence for ischemic and hemorrhagic stroke, subdural hematoma, neoplasm, arteriovenous malformation, micro and macrohemorrhages, superficial siderosis, lacunar infarcts, white matter abnormalities, and vasogenic edema. The imaging sequence for the Screening/safety MRI will include: T2 weighted anatomic MRI to rule out major white matter changes, cerebral infarction or other structural lesions, and a high-resolution 3D T1-weighted scan with isotropic voxels with volumes of 1 mm³ or less. In addition, both FLAIR for the detection of vasogenic edema and T2 Gradient Recall Echo for the detection of microhemorrhages will be acquired. The 3D dataset will be reconstructed in transverse slices in Digital Imaging and Communications in Medicine format. The results of this MRI assessment will also be used as the Baseline Period MRI, against which changes after drug administration will be compared. Further details of the MRI protocol can be found in the Imaging Acquisition Guideline. MRI acquisition and interpretation will be organized centrally to ensure reproducibility and consistency between units involved. MRI imaging will be conducted on separate days from the scheduled visits. MRI imaging should be conducted within the 7 days before Visits 14, 16, 18, 20, 32, and 38. (revised per Amendments 04, 07, and 08) In the event of an UNS Visit, the investigator in consultation with the sponsor will determine whether or not a safety MRI should be conducted. If an ED Visit takes place, an MRI is to be conducted if not already performed during the preceding 90 days. If subjects have non-MRI compatible devices fitted during treatment, then a computed tomography scan may be utilized to assess safety, if deemed appropriate by the investigator. (revised per Amendment 08)

At any time during the Treatment Period, subjects will be discontinued from study drug if they develop any of the following features on MRI: vasogenic edema, macrohemorrhage, an area of superficial siderosis, or a symptomatic microhemorrhage. All of these features must be reported as study specific AEs (or AEs of special interest). These subjects will undergo an ED Visit within 7 days after study drug discontinuation as well as 4 Follow-up Visits at 2, 4, 8 and 12 weeks after the last dose of Core Study treatment or 2 Follow-up Visits at 4 and 12 weeks after the last dose of Extension Phase treatment. (revised per Amendments 04 and 07) Subjects will also undertake an UNS Visit (with MRI) at approximately 30 days after the visit at which such MRI features were first identified. Additional visits may be arranged if clinically indicated in the opinion of the investigator, and may occur later than 12 weeks after the final dose of study drug.

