Elenbecestat (E2609) tablets of 5-, 10-, and 25-mg dose strengths will be supplied. Placebo tablets to match elenbecestat will be of identical appearance. Each subject will receive 2 tablets, which when combined will make up the required doses of elenbecestat or placebo, to be administered orally QD with food. (revised per Amendment 05)

Study Treatments (Extension Phase) (revised per Amendments 07 and 08)

Elenbecestat tablets of 50-mg dose strengths will be supplied during the Extension Phase. Each subject will take 1 tablet orally QD, with or without food.

Duration of Treatment

Core Study

The maximum duration of a subject's participation in the study will be approximately 2 years, comprising the following:

- Screening and Baseline Periods (Prerandomization Phase): up to 60 days, plus an additional window of up to 30 days if required (revised per Amendment 02)
(In subjects who have an active infection within 4 weeks of the planned randomization date, the duration of the pre-randomization phase can be extended by up to 4 weeks to allow additional time for resolution of the infection.)
- Treatment Period (Randomization Phase): up to 78 weeks
- Follow-up Period (Randomization Phase): 12 weeks (post last dose)

Extension Phase (revised per Amendments 07 and 08)

The duration of the Extension Phase will be approximately 220 weeks, comprising the following:

- Treatment Period: up to 208 weeks (48 months)
- Follow-up Period: 12 weeks (after the last dose)

Concomitant Drug/Therapy (Core Study and Extension Phase) (revised per Amendments 04 and 07)

The following agents are not permitted before randomization (specific timeframes are shown below) and throughout the study until after the last treatment visit in the Core Study (for subjects participating in the Core Study only) or the last treatment visit in the Extension Phase (for subjects participating in the Extension Phase) (see [Appendix 2](#) for a detailed listing of these agents) (revised per Amendment 07):

- Drugs that may cause QTc prolongation are not permitted for a period of 5 half-lives or 14 days (whichever is longer) before randomization.
- Strong CYP3A4 inhibitors are not permitted for a period of 5 half-lives or 14 days (whichever is longer) before randomization.
- Live vaccines are not permitted within 3 months before randomization. This does not apply to non-live/inactivated vaccines.
- Ig therapy and biologic drugs are not permitted within 6 months before randomization.

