The primary reason for discontinuation and all other reason(s) contributing to the subject's discontinuation from study drug should be collected on the ED from study drug electronic case report form (eCRF) page (see Protocol [Section 9.5.5](#)). In addition, the date of last dose of study drug will be recorded on the Study Drug Dosing eCRF page.

Safety-related criteria for discontinuation of study drug include the following:

1. Absolute lymphocyte count will be monitored during the study. Should a subject develop lymphocytopenia (less than $800/\text{mm}^3$ or LLN, whichever is higher), a confirmation test should occur as soon as possible but no later than within 5 days with a repeat test of absolute lymphocytes. If confirmed, study drug administration should be interrupted for a minimum period of 2 weeks. Restart of study drug may take place only when absolute lymphocyte count returns to greater than LLN. Absolute lymphocyte count will be measured 4 weeks after restart of study drug. Subsequent measurements of absolute lymphocyte counts will follow the schedule of assessments and any results showing a Grade 2 or greater lymphocytopenia (less than $800/\text{mm}^3$) should be handled as above. If a 2nd occurrence of Grade 2 or greater lymphocytopenia (less than $800/\text{mm}^3$), that is confirmed on repeat testing, occurs within 6 months, then the subject should be discontinued permanently from the study drug.
2. A subject with any skin rash of moderate to severe intensity, or any rash lasting more than 72 hours regardless of severity (with the exception of oral or genital herpes as described in the next paragraph), will be discontinued from study drug and a dermatologic consult will be requested regardless of whether the rash is considered drug-related or due to other causes. For cases where the investigator suspects a drug rash, regardless of severity, the subject will be discontinued from study drug, a dermatologic consult will be requested, and a skin biopsy will be performed to confirm the diagnosis. The skin rash will be treated as per standard care and will be followed up until resolution regardless of etiology or severity.
3. Subjects who develop moderate to severe oral or genital herpes should be discontinued from study drug. Subjects who develop a mild case of oral or genital herpes may remain on study drug even if the event lasts more than 72 hours.
4. Pregnancy

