5. A postdose ECG with a QTcF interval increase from baseline >60 msec and a QTcF interval >450 msec as demonstrated from triplicate ECGs
6. Subjects who develop of any of the following features on MRI should be discussed with the medical monitor: vasogenic edema, macrohemorrhage, an area of superficial siderosis, or a symptomatic microhemorrhage. If discontinued from study drug, subjects will undergo an ED Visit within 7 days after discontinuation. They will also undertake an Unscheduled (UNS) Visit (with MRI) at approximately 4 weeks after the visit at

which such MRI features were first identified. Additional visits for safety may be arranged if clinically indicated in the opinion of the investigator, including after 12 weeks after the last dose of study drug. At any time during the Treatment Period, subjects who have asymptomatic, treatment-emergent microhemorrhages as detected by MRI, but none of the features which merit discontinuation of treatment (ie, vasogenic edema, macrohemorrhage, an area of superficial siderosis, or a symptomatic treatment-emergent microhemorrhage) may continue with treatment. These subjects will have safety assessments (including MRI) at approximately 4 weeks after the visit at which such MRI features were found. They will also continue with the scheduled MRI scans. Additional unscheduled MRI scans may be arranged on an individual subject basis in discussion with the study medical monitor.

7. Subjects who have postdose ECG with an average QTcF interval >500 msec from triplicate ECGs should be discussed with the medical monitor.

Treatments

During the Extension Phase, all subjects will receive open-label elenbecestat 50 mg once daily (QD). Each subject will take 1 tablet orally QD, with or without food. Please refer to [Table 14](#) for specific information on drug administration on days when PD sampling is to be performed.

EXTENSION PHASE ASSESSMENTS

Safety assessments will continue to be monitored according to the Schedule of Assessments and all adverse events (AEs) and serious adverse events (SAEs) recorded. All safety assessments (eg, physical examinations, neurological examinations, vital signs, hematology, blood chemistry, serum and urine pregnancy test for females of childbearing potential, safety MRI and vMRI) will be performed as described in [Table 14](#). The number of blood samples and the total volume of blood that will be collected throughout Extension Phase are summarized in [Table 13](#).

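### For the same four MRI findings in the Extension Phase, Protocol Section 9.5.1.5.7 requires study drug to be stopped, while Appendix 6 item 6 asks only for discussion with the medical monitor

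*Protocol*

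**What the plan says.** Section 9.5.1.5.7 makes stopping mandatory: "At any time during the Treatment Period, subjects will be discontinued from study drug if they develop any of the following features on MRI", followed by the four features (vasogenic edema, macrohemorrhage, superficial siderosis, symptomatic microhemorrhage). For subjects stopped in this way it provides an Early Discontinuation Visit and then either the four Core Study follow-up visits or "2 Follow-up Visits at 4 and 12 weeks after the last dose of Extension Phase treatment". It also calls for an unscheduled visit with MRI about 30 days after the visit at which the finding was first identified.

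Appendix 6 governs the Extension Phase. Under the lead-in "Safety-related criteria for discontinuation of study drug include the following", item 6 reads: "Subjects who develop of any of the following features on MRI should be discussed with the medical monitor", and names the same four features. It continues: "If discontinued from study drug, subjects will undergo an ED Visit within 7 days after discontinuation". It then allows subjects with asymptomatic treatment-emergent microhemorrhages to continue if they have "none of the features which merit discontinuation of treatment", and lists the four features again in parentheses. Its unscheduled MRI visit is at about 4 weeks.

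Section 9.3.3 ends by saying that the Extension stopping criteria are to be found in Appendix 6. Section 9.2.5 names MRI changes among the subjects on which discontinuation criteria are based in both phases.

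**The concern.** An investigator whose Extension subject has one of these findings meets two instructions in the current protocol. One says the subject stops. The other says the case is discussed, and leaves open whether the subject stops. Both cannot be followed as written: a subject kept on drug after discussion complies with Appendix 6 item 6 and departs from Section 9.5.1.5.7.

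What is at stake is first the clarity of a subject-safety instruction. The consequence of acting on either passage is also hard to undo. Section 9.5.5 does not let a subject who discontinues early restart study drug, as distinct from one whose dosing is temporarily suspended under medical monitor guidance.

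**Working it through.** No arithmetic is needed for the contradiction itself. The check has four steps.

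**1. Are the findings the same?** Yes. Both passages name the same four MRI features.

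**2. Do both passages apply to the Extension?** Appendix 6 does by its title. Section 9.5.1.5.7 does for three reasons:
- Its follow-up sentence provides for subjects stopped in the Extension ("2 Follow-up Visits at 4 and 12 weeks after the last dose of Extension Phase treatment").
- Its scan schedule runs into the Extension: "MRI imaging should be conducted within the 7 days before Visits 14, 16, 18, 20, 32, and 38". Visits 32 and 38 are the Month 24 and Month 48 Extension visits.
- The term on which its stopping sentence depends is also used for the Extension, as in the Synopsis: "Treatment Period: up to 208 weeks (48 months").

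**3. Is the required action the same?**

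| | Section 9.5.1.5.7 | Appendix 6 item 6 |
|---|---|---|
| Action on the finding | Subject is discontinued | Case is discussed with the medical monitor |
| Status of stopping | Mandatory | Conditional ("If discontinued from study drug, subjects will undergo an ED Visit within 7 days after discontinuation") |
| Further description of the features | None | Still said to merit discontinuation, under a heading of discontinuation criteria |
| Unscheduled MRI visit | About 30 days | About 4 weeks |

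The weight lies on the first row. The conditional phrase in the second row would prove little alone, because the Core Study criterion in Section 9.3.3(f) uses the same phrase in a list where the features are plainly stopping criteria. In Appendix 6 it follows an instruction to discuss, so there it does leave the outcome open.

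The last row is minor: 4 weeks × 7 = 28 days, so the two timings differ by 2 days and both are approximate. Section 9.3.3(f) also uses about 4 weeks, so Section 9.5.1.5.7 is the odd one out.

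**4. Does any text decide between them?** Section 9.3.3 says where the Extension criteria are, and Section 9.1.3 says Appendix 6 holds the complete description of that phase. Neither says that Appendix 6 prevails over Section 9.5.1.5.7, and neither confines that section to the Core Study.

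**The case against.** The strongest reply is that the protocol tells the reader where to look. Sections 9.3.3 and 9.1.3 both direct the Extension reader to Appendix 6, and Section 9.5.1.5.7 is an imaging section, not the list of stopping rules. This stands in part, because the signpost reduces the ambiguity. But a signpost is not a precedence clause, and a site acting on an MRI result has good reason to open the Safety MRI section, whose mandatory wording reaches the Extension. Appendix 6 does not settle the matter either, since item 6 keeps the description "none of the features which merit discontinuation of treatment".

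A second reply is that practice would be more uniform than the text. MRI reading is central, and Section 9.5.1.5.1 already requires a detailed description of these events for the medical monitor. This also stands in part. The monitor would be informed under either reading, so it is right to say that sites could diverge, not that they would. Being informed, however, is different from deciding whether the subject stops.

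A third reply is that the revision history for Amendment 08 records removal of the stopping requirement, with Appendix 6 as the only affected section. That suggests how the conflict arose. It does not change the current wording of Section 9.5.1.5.7, and the finding rests on current text alone.

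Four stronger readings are tempting and are not supported:
- **A third conflicting rule in Section 9.2.5.** That bullet lists topics and prescribes no action. Appendix 6 item 6 is an MRI item under a discontinuation heading, so the list does not contradict it.
- **A percentage effect on discontinuation rates.** One might divide one or two cases by 48 to 72 subjects (60 × 0.8 = 48; 60 × 1.2 = 72). That range is the number randomized to the Core Study. Entry to the Extension requires Core completion, further eligibility and the subject's choice, so its size is not known from the protocol. No frequency of these findings is given either.
- **Damage to the Extension's primary endpoint through discontinuation counts or exposure.** The endpoint lists adverse events, MRI parameters and other safety measures. It names neither discontinuations nor exposure after a finding. The phase is open-label, single-arm and descriptive, so no comparison is at risk.
- **A need for a new data field.** Reasons for stopping are already collected on the case report form, and event, treatment and outcome details under Section 9.5.1.5.1.

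**Conclusion.** The protocol is wrong as written on this point. For vasogenic edema, macrohemorrhage, superficial siderosis or symptomatic microhemorrhage in the Extension Phase, Section 9.5.1.5.7 mandates stopping and Appendix 6 item 6 mandates only discussion, while retaining language that points the other way. The conclusion rests on current text and on the absence of any statement of precedence. It needs no numerical assumption.

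Its reach is every Extension subject with such a finding on a scheduled, early-discontinuation or unscheduled scan. How many that would be cannot be derived from the protocol. The case for correcting it rests on subject safety and clear instruction to sites, not on any calculated effect on the results. No view is offered on which rule is clinically right.

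**What to change.** Reconcile Section 9.5.1.5.7 with Appendix 6 item 6 so that a single Extension rule for the four features is stated once and cross-referenced elsewhere. In the same edit:
- Bring the wording in item 6 that says the features merit discontinuation into line with the chosen rule.
- State one timing for the unscheduled MRI visit in place of about 30 days and about 4 weeks, and check it against Section 9.3.3(f).
- Check the summary list in Section 9.2.5 against the result.
- Notify sites of the reconciled rule.

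The choice of rule belongs to the sponsor's clinical and safety staff. The cost is a wording correction in a protocol amendment and one communication to sites. No new data collection is needed.
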